## **4 STUDY DESIGN AND MANAGEMENT OVERVIEW**

### **4.1 Study Design Overview**

The primary null hypothesis of this randomized, double-blind multicenter clinical trial is, there

is no difference in 90-day risk of any new stroke (ischemic or hemorrhagic) in those treated with a 3-month regimen of clopidogrel initiated with a loading dose of 300 mg followed by 75 mg/day combined with aspirin 75 mg/day during the first 30 Days versus a 3-month regimen of aspirin 75 mg/day alone when initiated within 24 hours of symptom onset in high-risk patients with TIA or minor stroke.

Patients with high-risk TIA (defined as an ABCD score  $\geq 4$ ) or minor ischemic stroke (defined as an NIHSS  $\leq 3$ ), who can be treated within 24 hours of symptom onset will be enrolled. Patients meeting these criteria and offering informed content will be randomized into two groups: the first group will receive a 300mg loading dose of clopidogrel on the day of randomization, followed by 75 mg clopidogrel/day from Day 2 to 3 months. Aspirin will be given in a total dose ranging between 75 mg and 300 mg (open label with dose determined by the treating physician) on the first day, followed by blinded 75 mg once /day from Day 2 to 30. Between day 31 and 3-month visits, aspirin 75 mg will be replaced by a placebo of aspirin 75 mg. The second group will receive open label aspirin in a total dose ranging between 75 mg and 300 mg on the first day, followed by 75 mg once/day from Day 2 to 3 months. A placebo for clopidogrel will be given from the day of randomization until the 3-month visit. Subjects will be followed for 90 days and risk of any stroke (ischemic or hemorrhage) will be assessed in the treatment groups. The trial will be completed in 35 months, with 3,800 subjects recruited from about 80 centers in China in partnership with research network and CHANCE Clinical Research Collaboration. A Data and Safety Monitoring Board (DSMB) will regularly monitor safety during the study.

#### **4.2 Study Milestones**

A 3-year budget and recruitment plan have been created; key study milestones below.

##### **STUDY MILESTONES**

Pre-enrollment Study Initiation 9 months (2009.01-2009.09)

---

Recruitment and Follow-up	19 months (2009.10- 2011.04)
Completion of Follow-up	3 months (2011.05-2011.07)
Data Analysis and Publication	4 months (2011.08-2011.11)
Total Duration	35 months

### **Executive committee**

The two co-chairs and additional members of the Steering Committee, including two project directors, will be members of the Executive Committee. They will convene more frequently (teleconferences or physical meetings) to review the status of the trial and available blinded data and will take appropriate actions regarding the conduct of the study.

A face-to-face Executive Committee meeting will be organized to make major decisions.

The composition of the Executive Committee and its responsibilities are described in a charter which will be finalized before the start of the trial.

### **Data safety and monitoring board (DSMB)**

The DSMB will meet regularly and monitor the progress of the CHANCE study to ensure that the study meets the highest standards of ethics and patient safety. It is composed of

Academic Members, including an independent statistician, who are not otherwise participating in the trial. A DSMB charter including membership role and responsibilities will be approved by both the DSMB and the Executive Committee before the start of the trial.

Written recommendations and their rationale will be provided to the Chairs of the Steering Committee immediately after each DSMB meeting.

DSMB members: [name], [name], [name].

### **Adjudication committee**

Clinical outcome events (stroke, MI, death, overt bleedings) will be reviewed by independent experts (neurologists, cardiologists). An adjudication committee charter including membership, role and responsibilities will be approved before the start of the trial by the Adjudication Committee and the Executive Committee.

Neuroimaging associated with clinical events will be read locally and reports will be included in adjudication packets. The adjudication committee may request actual images from sites or from the core lab in special instances.

Adjudication committee member: [name], [name], [name]

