#### 4.6.3.4 Safety Endpoint

##### 4.6.3.4.1 Primary safety endpoints

- ✧ Incidence of severe bleeding or moderate bleeding (GUSTO definition, see appendix 6), including fatal bleeding and symptomatic intracranial hemorrhage

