##### 4.6.3.4.1 Secondary safety endpoints

- ✧ Incidence of symptomatic and asymptomatic intracranial hemorrhagic events at 3 months
- ✧ Total mortality
- ✧ AEs/SAEs reported by the investigators

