Appendix 6: GUSTO classification

Severe Bleeding	Documented intracranial hemorrhage or bleeding that causes hemodynamic compromise requiring blood or fluid replacement, inotropic support, ventricular assist devices, surgical intervention (other than vascular site repair), or CPR to maintain a sufficient cardiac output.
Moderate Bleeding	Bleeding that requires transfusion of blood but does not lead to hemodynamic compromise requiring intervention.
Mild Bleeding	Bleeding not requiring transfusion and not causing hemodynamic compromise. This includes subcutaneous bleeding, mild hematomas, oozing from puncture sites, etc.

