#### **Safety Endpoint**

- Rate of moderate and severe bleeding incidence (GUSTO definition), including fatal bleeding and symptomatic intracranial hemorrhage
- Rate of symptomatic and asymptomatic intracranial hemorrhagic events at 3 months
- Rate of total mortality
- Incidence of AEs/SAEs (as described in the protocol) reported by the investigators

Clinical safety will be assessed by a physical examination including neurological evaluation at Day 1, D21 and D90 visits. Adverse events will be collected at each visit after baseline. Supine blood pressure and heart rate will be measured at each visit. No specific laboratory safety tests are required during this study. However, if a laboratory abnormality is clinically relevant or leads to an adverse event report, specific appropriate actions may be required (see Appendix 5, decision charts). An ECG will be performed at the baseline visit (Day 1).

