### Adverse Events

Adverse events (AEs) will be coded using the MedDRA coding dictionary (Version 6.0 or a later release) and grouped by system organ class (as detailed in the study protocol). Separate data display listings and summaries will be presented for adverse events that start prior to first dose of study medication (pre-treatment), whilst on study medication (during treatment) and after the last dose of study medication (post-treatment).

Within each treatment group, the number and percentage of subjects experiencing an AE will be summarized by system organ class and preferred term and Fisher's Exact test will be used to compare the number of each grouped AE event between treatment groups. In addition, a separate summary will be provided for AEs experienced by more than 5% of subjects in either of the treatment groups.

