### **裁决委员会**

临床终点事件（卒中、心肌梗死、死亡、大出血）将由试验之外的专家（神经科专家、心脏病专家）进行复审。

裁决委员会成员资格（包括资格、角色、职责）应在试验开始之前经由裁决委员会和执行委员会认证。

与临床相关事件的神经影像将首先在分中心阅读，在裁定文件中将包括影像报告。在特殊情况下，裁决委员会可能将要求分中心或中心实验室递交原始影像文件。

裁决委员会成员：[name]（香港），[name]（美国），[name]（美国），[name]，[name]，[name]

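### Bleeding is graded mild, moderate or severe, but no planned analysis compares the number of patients with any bleed between arms

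*Supplement*

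**What the plan says.** **Collection and review.** Section 8.3.1 of the final protocol has adverse events recorded whatever their seriousness. The adjudication committee text in section 4.3 reads: "Clinical outcome events (stroke, MI, death, overt bleedings) will be reviewed by independent experts (neurologists, cardiologists". Section 4.4 requires investigators to be certified in GUSTO. Appendix 6 defines three grades; the mild one begins: "Bleeding not requiring transfusion and not causing hemodynamic compromise".

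**Endpoints.** The primary safety endpoint (final protocol, 4.6.3.4.1) is: "Incidence of severe bleeding or moderate bleeding (GUSTO definition, see appendix 6), including fatal bleeding and symptomatic intracranial hemorrhage". The secondary list has: "Incidence of symptomatic and asymptomatic intracranial hemorrhagic events at 3 months", followed by total mortality and AEs/SAEs. The final SAP, under Safety Endpoint, has: "Rate of moderate and severe bleeding incidence (GUSTO definition), including fatal bleeding and symptomatic intracranial hemorrhage". The mild grade enters no endpoint.

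**Analysis.** Under Adverse Events, the final SAP says: "the number and percentage of subjects experiencing an AE will be summarized by system organ class and preferred term". It compares each grouped event between arms with Fisher's exact test.

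**Chinese final protocol.** The adjudication text lists: "临床终点事件（卒中、心肌梗死、死亡、大出血". The last item means major bleeding, where the English has overt bleeding. The Chinese primary safety endpoint is severe bleeding only, where the English has severe or moderate.

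**The concern.** The tested arm receives clopidogrel with aspirin through day 21, and the protocol gives bleeding risk its own subsection (2.2.4.4). Bleeding is the main harm to look for. The named bleeding endpoints use only the less frequent, more serious grades.

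The adverse-event tables do not replace a pooled count, for three reasons:
- Nasal, gastrointestinal, urinary and skin bleeds fall in different rows, each tested alone.
- A patient with two kinds of bleed appears in two rows, so adding rows does not give a count of patients.
- Section 8.2 generally keeps efficacy endpoints out of the adverse events. Hemorrhagic stroke is part of the primary efficacy endpoint, so it would usually be missing from those rows.

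At stake is whether the report can say how many patients bled in each arm, with an interval around the comparison. Section 10.1.1.1.2 already says that no excess of intracerebral or life-threatening bleeding is expected. A wide, non-significant comparison of serious bleeds could be taken as support for that while total bleeding goes uncompared.

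**Working it through.** **1. The plan's own figure.** Inputs (final protocol, 10.1.1): control stroke risk 0.14, relative risk 0.78, two-sided 5%, power 90%. The treated risk is 0.14 × 0.78 = 0.1092, and the mean of the two is 0.1246.

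n per arm = [1.96·√(2·0.1246·0.8754) + 1.2816·√(0.14·0.86 + 0.1092·0.8908)]² / 0.0308² = 2,415, so 4,830 in total. This matches Table 2. Adding 5% gives 4,830 × 1.05 = 5,072, also as stated, rounded up to 5,100. The size is set on stroke; no power is stated for bleeding.

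**2. Power for bleeding with the same method.** With n = 2,550 per arm, control rate p₁ and treated rate p₂ = p₁·RR:

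power = Φ{(p₂ − p₁ − 1.96·SE₀)/SE₁}, where SE₀ = √(2·p̄(1 − p̄)/n) and SE₁ = √([p₁(1 − p₁) + p₂(1 − p₂)]/n).

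Example, p₁ = 0.5%, RR 1.5: p₂ = 0.75%, SE₀ ≈ SE₁ ≈ 0.00221, so (0.0025 − 0.00433)/0.00221 = −0.83 and power is 20%.

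Example, p₁ = 3%, RR 1.5: p₂ = 4.5%, SE₀ ≈ SE₁ ≈ 0.00532, so (0.015 − 0.01043)/0.00532 = 0.86 and power is 81%.

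All control rates below are assumptions.

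| Aspirin-arm rate | Power, RR 1.5 | Power, RR 1.5, Fisher (simulated) | Power, RR 2 | RR detectable with 80% power |
|---|---|---|---|---|
| 0.3% | 14% | 9% | 36% | 3.03 |
| 0.5% | 20% | 17% | 54% | 2.46 |
| 1.0% | 36% | 31% | 84% | 1.95 |
| 2.0% | 63% | 60% | 99% | 1.63 |
| 3.0% | 81% | 79% | >99% | 1.50 |

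The first three rows are a plausible range for moderate or severe bleeding. The last two are one for any bleeding; if any bleeding is only 1%, the 1.0% row applies. Taking 5% off the sample (2,422 per arm) lowers the RR 1.5 figures by at most about 2 points.

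**3. A case that goes the other way.** Two trials cited in sections 2.2.4.1 and 2.2.4.2 are reported with a one-point absolute excess in major bleeding on the combination. With that excess in moderate or severe bleeding here, power is 99%, 95% and 84% at control rates of 0.2%, 0.5% and 1.0%.

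**4. If mild bleeds do not rise.** Take 0.5% moderate or severe bleeding with RR 1.5, plus 1.5% mild bleeding with RR 1. Any bleeding goes from 2.0% to 0.75% + 1.5% = 2.25%. SE₀ ≈ SE₁ ≈ 0.00404, so (0.0025 − 0.00792)/0.00404 = −1.34 and power is 9%, below the 20% for moderate or severe bleeding alone. The gain therefore depends on mild bleeds rising too.

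**The case against.** The strongest reply is that confining the named endpoint to clinically important grades, and leaving lesser bleeds to adverse-event reporting, is a coherent choice. Mild bleeds are more subjective and matter less. That stands, and it is why the added endpoint should be secondary.

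Three stronger readings are tempting, and the documents do not support them:

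- **That every overt bleed is adjudicated.** The English text lists overt bleeding without saying all, and the Chinese says major bleeding. The event packets described in section 9.4 cover neurological and cardiac events; none is described for bleeding. So a reader cannot assume that graded, adjudicated data exist for every mild bleed.
- **That mild bleeds are not compared at all.** They are, term by term, by Fisher's exact test, and hemorrhagic stroke has its own Cox analysis. What is missing is the pooled count of patients.
- **That the trial has little power to show bleeding harm.** This depends on assumed rates and relative risk. It fails for a one-point absolute excess. That figure comes from other settings, one of them mostly procedure-related, so it settles nothing either way.

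**Conclusion.** The omission is real in the final protocol and final SAP: no planned analysis gives a between-arm comparison of patients with any bleed, although a mild grade is defined and all adverse events are recorded.

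If moderate or severe bleeding runs at 0.3–1.0% and the relative risk is 1.5 for all grades, power is about 14–36% for the planned endpoint, against 63–81% for any bleeding at 2–3%. The advantage shrinks or reverses if any bleeding is rare or mild bleeds do not increase. It is not needed for detection if the excess in serious bleeding is as large as one percentage point. The documents give no rate that would choose between these cases.

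A related gap lies beside it: the SAP's Safety Analyses section names no model or test for the moderate or severe bleeding endpoint.

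This is a cheap improvement. It does not touch the primary efficacy analysis or the sample size.

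**What to change.** - Add any bleeding (GUSTO mild, moderate or severe) to the secondary safety endpoints in protocol 4.6.3.4.1 and to the SAP's Safety Endpoint list: ITT population, time to first bleed within 90 days, with counts by grade and arm.
- Report a hazard ratio with 95% CI from a Cox model of the form in the SAP's Main Model section, with pooled center as a random effect. Specify the same model for moderate or severe bleeding, so that the secondary endpoint is not analyzed more fully than the primary safety endpoint.
- Use the adjudicated grade where there is one and the investigator-reported grade otherwise, and show how many bleeds come from each source.
- Reconcile the English and Chinese final texts on which bleeds are adjudicated and on whether the primary safety endpoint includes moderate bleeding.

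The cost is one more model and table, plus grading from investigator reports where bleeds were not adjudicated. The drawback is the subjectivity of mild bleeds; double blinding should keep their reporting balanced between arms, and secondary status limits the weight they carry.

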### **4.4 Site Training, Certification, and Update**

Executive committee have already provided training to their sites in Good Clinical Practice Guidelines and in some outcome assessments (e.g., NIHSS, mRS).

Prior to initiation of patient enrollment, Site Investigators and Coordinators will complete training programs and their certifications. In these training modules, the patient selection criteria and follow-up procedures will be reviewed. Case studies illustrating potential problems in adhering to study protocol and blinding will be discussed.

All investigators must complete the following training modules, and receive certification:

- Study procedures
- Primer on the diagnosis of TIA and its mimics

- Use of the ABCD score
- CHANCE eligibility
- Modified Rankin Scale
- NIHSS
- SSS-TOAST
- EQ-5D
- Outcome events adjudication
- GUSTO
- Collecting blood sample only for subgroup
- Collecting DICOM imaging data only for subgroup

Successful completion of the training program will be required before a site is certified to enroll patients. Telephone-based meetings, with the PI and key staff available to address questions, will occur intermittently. Certification of competence will be obtainable on the four training centers.

A detailed Manual of Procedures will serve as the primary document describing all study related procedures. It will serve as a guide for training of clinical center personnel and will be updated periodically throughout the study on the CHANCE website, as needed. A system composed of members of executive committee and clinical research associate will be implemented for the clinical centers to call, fax, or e-mail any procedural questions regarding the study. The CHANCE executive committee will formulate answers in consultation with the Steering Committee, and will periodically distribute to the participating centers a set of frequently asked questions (FAQ) and answers. These questions and answers will be available on the study website.

The members of executive committee will manage and conduct site visits for its sites and ensure the integrity and validity of the data recorded on the Case Report Forms. Each site will be visited at least once during the trial, and as needed if questions about data quality or

problems with recruitment arise.

#### **4.5 Contact Schedule and Measurements**

Subject encounters will include screening, randomization, hospital discharge, 30th day visit, and 90th day visit or a final event visit. In addition, event visits are to occur whenever patient contact suggests that a patient experiences a potential clinical neurological event, including a clinical deterioration that could be possibly related to ischemia, or new transient or persistent neurological symptoms, an adjudication packet will be produced by the site within 72 hours.

#### **4.6 Outcomes**

The definitions of endpoint outcomes are given in Appendix 1.

##### **4.6.1 Primary Efficacy Endpoint**

Percentage of patients with the 3-month new vascular events, defined as any event of the following:

✧ *Any stroke (ischemic or hemorrhagic)*

##### **4.6.2 Secondary Efficacy Endpoint**

- Percentage of composite of any stroke, myocardial infarction, and vascular death within 3 month.
- Patients with the 3-month new clinical vascular events (ischemic stroke/ hemorrhagic stroke/ TIA/ MI/ vascular death) evaluated individually.
- Modified Rankin Scale score changes (continuous) and dichotomized at percentage with score 0-2 vs. 3-6 at 3 month follow-up (Scale is described in Appendix 2).
- Further efficacy exploratory analysis:
  - ✧ Impairment (changes in NIHSS scores at 3 month follow-up), (Scale is described in Appendix 3).

- ✧ Quality of Life (EuroQol EQ-5D scale, described in Appendix 4).
- Efficacy endpoint will also be analyzed stratified by etiological subtypes (non-ICAD vs. ICAD), by qualifying event (TIA vs. minor stroke), and by age (<65 years vs ≥65 years).

#### 4.6.3 Safety Endpoint

##### 4.6.3.1 Clinical Safety

Clinical safety will be assessed by:

- ✧ A physical examination including neurological evaluation at D1, hospital discharge, M1 and M3 visits.
- ✧ Adverse event collection at each visit after baseline
- ✧ Measurement of supine blood pressure and heart rate at each visit.

##### 4.6.3.2 Adverse Event Collection

No specific laboratory safety tests are required during this study. However, if a laboratory abnormality is clinically relevant or leads to an adverse event report, specific appropriate actions may be required (see Appendix 5, decision charts).

##### 4.6.3.3 Electrocardiogram

An ECG will be performed at the baseline visit (Day 1).

##### 4.6.3.4 Safety Endpoint

###### 4.6.3.4.1 Primary safety endpoints

- ✧ Incidence of severe bleeding or moderate bleeding (GUSTO definition, see appendix 6), including fatal bleeding and symptomatic intracranial hemorrhage

###### 4.6.3.4.1 Secondary safety endpoints

- ✧ Incidence of symptomatic and asymptomatic intracranial hemorrhagic events at 3 months
- ✧ Total mortality

- 
- ◇ AEs/SAEs reported by the investigators

## **5 PARTICIPANT SELECTION**

During the course of the trial, about 80 sites will enroll 3,800 subjects with TIA or minor ischemic stroke. Before enrolling patients into the study, all collaborating sites will obtain approval from local Institutional Review Boards (IRBs), which will have access to all study documentation and educational materials.

### **5.1 Study Population**

#### Inclusion Criteria

- Adult subjects (male or female  $\geq 40$  years)
- Acute non-disabling ischemic stroke (NIHSS  $\leq 3$  at the time of randomization) that can be treated with study drug within 24 hours of symptoms onset. Symptom onset is defined by the “last see normal” principle.
- TIA (Neurological deficit attributed to focal brain ischemia, with resolution of the deficit within 24 hours of symptom onset), that can be treated with study drug within 24 hours of symptoms onset and with moderate-to-high risk of stroke recurrence (ABCD2 score  $\geq 4$  at the time of randomization). Symptom onset is defined by the “last see normal” principle.
- Informed consent signed

#### Exclusion Criteria

- Diagnosis of hemorrhage or other pathology, such as vascular malformation, tumor, abscess or other major non-ischemic brain disease (e.g., multiple sclerosis) on baseline head CT or MRI.
- Isolated or pure sensory symptoms (e.g., numbness), isolated visual changes, or isolated dizziness/vertigo without evidence of acute infarction on baseline head CT or

MRI.

- Modified Rankin Scale Score > 2 at randomization (pre-morbid historical assessment)
- NIH Stroke Score  $\geq$  4 at randomization
- Clear indication for anticoagulation (presumed cardiac source of embolus, e.g., atrial fibrillation, prosthetic cardiac valves known or suspected endocarditis).
- Contraindication to clopidogrel or ASA.
  - Known allergy
  - Severe renal or hepatic insufficiency
  - Severe cardiac failure, asthma
  - Hemostatic disorder or systemic bleeding
  - History of hemostatic disorder or systemic bleeding
  - History of thrombocytopenia or neutropenia
  - History of drug-induced hematologic or hepatic abnormalities
  - Low white blood cell ( $<2 \times 10^9/l$ ) or platelet count ( $<100 \times 10^9/l$ ).
  - Use of thrombolysis within 24 hours prior to randomization
- History of intracranial hemorrhage.
- Anticipated requirement for long-term non-study antiplatelet drugs, or NSAIDs affecting platelet function.
- Current treatment (last dose given within 10 days before randomization) with heparin therapy or oral anti coagulation.
- Gastrointestinal bleed or major surgery within 3 months.
- Planned or likely revascularization (any angioplasty or vascular surgery) within the next 3 months (if clinically indicated, vascular imaging should be performed prior to randomization whenever possible)

- Scheduled for surgery or interventional treatment requiring study drug cessation.
- Qualifying TIA or minor stroke induced by angiography or surgery.
- Severe non-cardiovascular comorbidity with life expectancy < 3 months.
- Women of childbearing age not practicing reliable contraception who do not have a documented negative pregnancy test.
- Currently receiving an investigational drug or device.

